6.0 DATA SAFETY REVIEW TEAM

6.1 Data/Efficacy Review

A Data Safety Review Team will be formed to evaluate the safety of the combination of the treatments as well as to objectively comment on any apparent decreased efficacy. The first three subjects will be treated at 100 mg rather than the full 200 mg every 3 weeks. Once the first three subjects have completed therapy and no adverse events have called for an earlier meeting, the Data Safety Review Team will meet to discuss the escalation of the dose to 200 mg. If one subject of the three subjects requires the dose of MK-3475 be withheld or discontinued, the 100 mg cohort will be expanded to 6 subjects. If two out of three or two out of six subjects develop toxicity that requires the dose to be withheld or discontinued, the dose will not be escalated to 200 mg MK-3475 every 3 weeks. All remaining subjects will be treated at 100 mg MK-3475 every 3 weeks for 6 cycles.

The Data Safety Review Team will again evaluate the patient safety and efficacy response after 7 and 10 subjects have completed the treatment regimen. The committee will also be charged with enforcing the stopping rules. All adverse event data, as well as patient response to treatment, will be presented to the committee and the committee will be allowed to

Product: MK-3475

Protocol/Amendment No.: Amendment 5, 21 October 2019

deliberate in a closed session to advise on the continued enrollment of subjects and to propose any protocol amendments to enhance the study.

Remainder of Page Intentionally Left Blank

Product: MK-3475

Protocol/Amendment No.: Amendment 5, 21 October 2019

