2.0 TRIAL DESIGN

2.1 Trial Design

This is a multicenter Phase I/II safety and efficacy study of MK-3475 (pembrolizumab) therapy used in combination with bladder infused BCG treatment for subjects, 18 years or older, with pathologically documented high risk superficial bladder cancer despite having received 2 courses of induction therapy or BCG treatment followed by maintenance BCG. Subjects will have confirmation of bladder cancer non-invasive to the muscle.

Approximately 20 subjects will be screened to treat 15 eligible subjects. Subjects will be enrolled to a single treatment group of a fixed dose of MK 3475 and BCG.

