5.2.4 Schedule Modification for Combination Therapy

The dosing schedule of the combination therapy will not be altered except on an individual drug basis (such as holding either individual BCG or MK-3475 therapy) if the time period is for 2 weeks or less. That is to say holding either of the two medications included in the combination therapy for less than two weeks should not affect the dosage schedule for the other medication. Patients will be discontinued from the trial if one of the two medications is held for more than 2 weeks because of toxicity. BCG treatment may continue, after a 2 week hold, outside of the study at the discretion of the treating Investigator.

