5.7 Subject Replacement Strategy

Subjects who have been screened and enrolled will be included in an intent-to-treat population. However, if a subject has been enrolled and subsequently treated or attempted treatment (IV insertion with MK-3475 preparation) with at least 1 cycle of MK-3475, the patient will not be replaced. If a screened subject withdraws prior to first treatment cycle, that subject may be replaced.

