5.8 Clinical Criteria for Early Trial Termination

Early trial termination will be the result of the criteria specified below:

1. Quality or quantity of data recording is inaccurate or incomplete
2. Poor adherence to protocol and regulatory requirements
3. Incidence or severity of adverse drug reaction in this or other studies indicates a potential health hazard to subjects

Stopping Rules:

The number of patients (15) planned for this study is not sufficient to represent the population as a whole nor is it sufficient to complete a powerful statistical analysis.

The first 3 subjects will be treated at 100 mg every 3 weeks for 6 cycles. If one subject of the three subjects requires the dose of MK-3475 be withheld or discontinued, the 100 mg cohort will be expanded to 6 subjects. If two out of three or two out of six subjects

develop toxicity that requires the dose to be withheld or discontinued, the dose will be not be escalated to 200 mg MK-3475 every 3 weeks. All remaining subjects will be treated at 100 mg MK-3475 every 3 weeks for 6 cycles.

For study subject safety, if there is any fatal toxicity or morbidity event related to the study treatment or procedures, or if one or more of the 15 subjects treated experience a grade 4 toxicity, then subject accrual will be suspended and all data pertaining to the events will be reviewed by the Study Investigators and Data Safety Review Team to determine if there is the need for any corrective actions.

Once that review is completed and any appropriate action is taken, subject accrual will begin again, if the Data Safety Review Team members have approved continuation of the study. If there is a second fatal treatment/morbidity event related to the study treatment or procedures, the study will be terminated. If 4 of 15 subjects experience grade 4 toxicities, the accrual will be suspended and reviewed for added appropriate measures. If 5 subjects experience grade 4 toxicity, the study will be terminated.

Non-local safety reports will be evaluated as they are received. Tabulations of the reports will be provided to the Data Safety Review Team with access to the full reports for completeness of review.

4. Plans to modify or discontinue the development of the study drug

In the event the investigational product is no longer available, ample notification will be provided so appropriate adjustments to subject treatment can be made.

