8.1.1.7 Assignment of Screening Number

Eligible subjects will be approached by consenting providers or research nurse to participate in this study. Subjects who do not meet the pathological criteria for enrollment will be considered a screen fail. Those subjects who meet pathological inclusion/exclusion criteria will be fully screened for other tests and procedures. Subjects will be assigned a 5-6 character ID code with the first three or four being the site code (a letter site code assigned to the site by the Sponsor) followed by a two digit number for a subject identifier beginning with 01 and each newly enrolled subject the subsequent number for that site. For example, SCI-03 would

Product: MK-3475

Protocol/Amendment No.: Amendment 5, 21 October 2019

represent the third patient enrolled at site SCI. Assigned subject numbers will only be used once. If a patient should be a screen failure, that number will be resigned and the next patient assigned the sequential number until enrollment is met. If a subject receives any part of the investigation treatment design and must discontinue treatment for any reason, they will not be replaced.

To register a subject, the following documents must be on file with the research nurse or data manager:

- Signed subject consent/HIPAA authorization form
- Copy of required laboratory test results
- Copy of the pathology report confirming high risk superficial transitional cell carcinoma histology
- Copy of the most recent history and physical dictation/record
- Any other documentation needed to verify inclusion/ exclusion criteria

The research nurse or data manager will verify eligibility with the Principal Investigator. To complete the registration process, the Project Manager will:

- Assign a subject study number
- Register the subject on the study

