8.1.6.6 Follow-up Visits

Subjects who complete all study treatment or discontinue trial treatment for a reason other than disease progression will move into the Follow-Up Phase and should be assessed at 19 week cystoscopy. Additional follow up information will be collected at 3, 6, 9, 12, 18, and 24 months post completion of treatment. Every effort should be made to collect information regarding disease status, start of new anti-neoplastic therapy, disease recurrence, disease progression, death, or end of the study. Information regarding post-study anti-neoplastic treatment will be collected if new treatment is initiated.

A final set of AUA IPSS and QOL questionnaires are also to be administered at the 3 month Follow Up visit.

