10.0 STATISTICAL ANALYSIS PLAN

10.1 Statistical Analysis Plan Summary

A minimum of 15 subjects will be enrolled. Seventy percent of bladder tumors are superficial [22] indicating to enroll at least 15 patients, approximately 21-25 patients will need to be approached to meet eligibility and to allow for patient disinterest.

Fifty percent of those patients who respond to BCG treatment develop recurrent disease [30; 31] generally detected within 6 months of BCG treatment. Those patients with recurrent disease often are sent for radical cystectomy as there are no other acceptable standard treatment options. This study, though primarily evaluating maximum tolerated dose, will examine the percent response at 19 weeks to determine if MK-3475 has altered the pattern of responders as early as 19 weeks from the start of treatment. The results of this study will not only examine the safety of combining MK-3475 with BCG for future studies, but will also assist in determining patient eligibility (recurrent superficial bladder cancer versus initial diagnosis) and considerations for future study design.

Patient related data will be collected and transferred to an excel spreadsheet for statistical analysis. SAS software version 9.4 will be used for all data analysis. Descriptive statistics will be computed for all study variables. Continuous variables will be described with measures of central tendency (mean, median) and dispersion (range, standard deviation). Categorical variables will be summarized as frequencies and percentages. Some examples include tumor stage (Ta, T1, Cis), age, ECOG Performance Scale (0, 1, 2), sex, and use of tobacco and alcohol.

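### The 7- and 10-subject safety reviews in Section 6.1 count subjects who completed treatment; read literally, early stoppers do not advance the count, so scheduled review slips as early stopping rises

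*Combined protocol and SAP*

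**What the plan says.** Section 6.1 has the Data Safety Review Team meet about escalation after the first three subjects, then review safety and efficacy again "after 7 and 10 subjects have completed the treatment regimen". It gives no calendar date, enrolment count or treated-subject count as an alternative trigger for those two later reviews. When the team meets, it is to see all adverse event data and patient responses, and it advises on continued enrolment.

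The planned size is 15. Section 2.1 says "Approximately 20 subjects will be screened to treat 15 eligible subjects"; Section 10.1 says "A minimum of 15 subjects will be enrolled", with no rule for going above that number. Replacement is ruled out once treatment has begun. Under Section 5.7, for a subject treated "with at least 1 cycle of MK-3475, the patient will not be replaced". Section 8.1.1.7 agrees: "If a subject receives any part of the investigation treatment design and must discontinue treatment for any reason, they will not be replaced".

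The protocol has several toxicity routes out of treatment. Section 5.2.4 states: "Patients will be discontinued from the trial if one of the two medications is held for more than 2 weeks because of toxicity". Table 3 and Section 5.2.1.1.3 add others, some of them below Grade 4.

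Completing and stopping early are distinct categories elsewhere. Section 8.1.6.6 moves into follow-up "Subjects who complete all study treatment or discontinue trial treatment for a reason other than disease progression", and footnotes b and c of the flow chart in Section 7.1 give the two groups different visits.

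Section 5.8 has event-driven review that ignores completion: "if one or more of the 15 subjects treated experience a grade 4 toxicity, then subject accrual will be suspended". The same suspension follows a related fatal or morbidity event.

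**The concern.** The primary objective is the safety of the combination, and the two later reviews are its only fixed checkpoints after the escalation decision. If only completers count, the clock runs on the subjects who tolerated treatment. Each early stop pushes a review back, and enough of them prevent it. The schedule then slows as treatment-ending toxicity becomes more common.

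What is at stake is mainly toxicity below Grade 4 that ends treatment. The numerical stopping rules in Section 5.8 count Grade 4 toxicities and related fatal or morbidity events. The two-of-three and two-of-six rule counts doses withheld or discontinued, but it governs only the decision to leave 100 mg. After escalation, no rule counts lower-grade discontinuations. A late review may also come too late to influence enrolment, which is part of the team's stated remit.

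**Working it through.** **No plan figure to reproduce.** The documents give no operating characteristics for these reviews and no expected completion rate. The early-stop rate *p* below is an assumption, shown over a range. It covers stopping for any reason, not toxicity alone.

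**Inputs from the documents.** 15 treated subjects (Sections 2.1 and 5.8); no replacement after treatment starts (5.7 and 8.1.1.7); triggers at 7 and 10 completers (6.1).

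**Chance that a review never occurs.** Let S be the number of early stoppers among 15 independent subjects, S ~ Binomial(15, *p*).

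- The 10-completer review is lost if fewer than 10 complete, that is S ≥ 15 − 10 + 1 = 6.
- The 7-completer review is lost if S ≥ 15 − 7 + 1 = 9.
- P(S ≥ k) = Σ from j = k to 15 of C(15, j) *p*^j (1 − *p*)^(15 − j).

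The mean number treated to reach k completers, with no cap on accrual, is k/(1 − *p*); for example 7/0.8 = 8.75.

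| Early-stop rate *p* | 7-completer review never occurs | 10-completer review never occurs | Mean treated for 7 (uncapped) | Mean treated for 10 (uncapped) |
|---|---|---|---|---|
| 10% | <0.1% | 0.2% | 7.8 | 11.1 |
| 20% | 0.1% | 6.1% | 8.8 | 12.5 |
| 30% | 1.5% | 27.8% | 10.0 | 14.3 |
| 40% | 9.5% | 59.7% | 11.7 | 16.7 |
| 50% | 30.4% | 84.9% | 14.0 | 20.0 |

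The uncapped means show the direction of delay only. At 50%, a mean of 14.0 does not put the 7-completer review at the 14th of 15 subjects: with 15 treated, it is never reached in about 30% of trials.

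**Timing illustration.** Section 1.0 gives a 60-month trial and 28 months per subject. I assume 60 − 28 = 32 months of accrual, even spacing of 32/14 = 2.29 months, and completion at week 19 (19 × 7/30.4375 = 4.37 months).

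- With no early stops, the reviews fall at 6 × 2.29 + 4.37 = 18.1 months and 9 × 2.29 + 4.37 = 24.9 months.
- Simulation (20,000 trials per rate) gives these mean times, among trials in which the review occurs:

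| *p* | 7-completer review (month) | 10-completer review (month) | All 15 already enrolled at the 10-completer review |
|---|---|---|---|
| 20% | 22.0 | 30.0 | 20% |
| 30% | 24.7 | 32.0 | 42% |
| 40% | 27.4 | 33.2 | 58% |

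**With the trigger changed.** If subjects who permanently stop also count, then under the same assumptions the reviews fall no later than months 18.1 and 24.9 whatever *p* is. Neither can be lost once 10 treated subjects have finished or stopped.

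**What the Grade 4 trigger catches.** At an assumed 10% Grade 4 rate, the chance of at least one event is 1 − 0.9^7 = 52% in the first 7 subjects and 1 − 0.9^15 = 79% in 15. That route is substantial, but it does not respond to lower-grade stops.

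**The case against.** The strongest objection is that completion is meant loosely. Section 6.1 also times the first review by the first three subjects completing therapy, yet it links that review to a rule counting subjects whose dose was withheld or discontinued. Section 5.2.3.1 describes the same meeting as following three subjects enrolled and treated. The texts that separate completers from stoppers concern visit scheduling. This stands to the extent that the term is ambiguous. A reader might infer that the plan definitely excludes early stoppers from the count; the documents do not settle that. They do not rule it out either, and the literal reading is the one a coordinator could apply.

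Second, a reader might infer that toxicity below Grade 4 reaches the team only through these reviews. That goes too far. Section 5.8 includes an undefined morbidity event and a general health-hazard criterion with no grade limit. Section 8.1.5.1 lets the team judge individual adverse events. Serious events go to the sponsor within 24 hours (9.1.3.1), and the sponsor monitors aggregate safety data (9.1.3.3). An earlier meeting is possible, though that text is written around the three-subject review. These routes are discretionary or without thresholds, so they narrow the gap without replacing a scheduled look.

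Third, a reader might think early stoppers' data are missing from the reviews. They are not: Section 6.1 already presents all adverse event data. The defect is timing, not content.

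Fourth, the large probabilities need 40 to 50% early stopping, for which the documents give no basis, and the minimum of 15 in Section 10.1 might allow more subjects. Both points are fair. The first limits the size of the concern; the second helps little without a rule for exceeding 15.

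**Conclusion.** The concern holds as a problem of wording and timing. Followed literally, the trigger delays the two later reviews as early stopping rises and, with enough of it, removes them: at least 6 of 15 stops for the 10-subject review and at least 9 of 15 for the 7-subject review. At early-stop rates of 20% or less, delay is the main effect; in the illustration it is about 4 months for the 7-subject review (22.0 − 18.1) and 5 months for the 10-subject review (30.0 − 24.9). At 30% and above, losing the 10-subject review becomes a real possibility. These sizes rest on 15 treated subjects, independence, a common assumed stop rate and, for the timing, even accrual over an assumed 32 months. The arithmetic is firm. Whether the authors intended the literal reading is uncertain, and the other safety routes confine the gap mainly to treatment-ending toxicity below Grade 4 after the escalation decision.

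**What to change.** In Section 6.1, change the trigger for the two later reviews to: *after 7 and 10 subjects have completed or permanently stopped study treatment*. If the authors already meant this, the edit simply records it. No further sentence on the data to be shown is needed.

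The change adds no patients or procedures and alters no dose or clinical rule. It has two costs. A review may be held that would otherwise never have taken place. And because these are also efficacy reviews, an earlier meeting may include fewer subjects with a Week 19 response. For a trial whose primary objective is safety, that is a reasonable exchange.

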7.0 TRIAL FLOW CHART

7.1 Study Flow Chart

Trial Period	Screening Phase	Treatment Week/Cycle											End of Treatment		Post Treatment
Treatment Week/ Title	Screening Visit ^a	1	4	7*	8*	9*	10*	11*	12*	13	16	19	Discontinuation	Safety FU 20	Follow-Up Visit
Scheduling Window (Days)	-28 to -1	+/- 3	+/- 3	+/- 1	+/- 1	+/- 1	+/- 1	+/-1	+/-1	+/- 3	+/- 3	+/- 3	At time of Discontinuation	30 days Post discontinuation	3,6,9,12,18,24 Post cyst
Administrative Procedures															
Informed Consent	X														
Inclusion/ Exclusion Criteria	X														
Subject Identification card ^e		X													
Demographics and Medical History	X														
Prior and concomitant Medication Review ^f	X	X-----X													
Post-study anti-cancer therapy status ^g															X
Recurrence status ^g													X		X
Questionnaires ^h		X					X					X			X
Phone Call ^h				X	X	X	X	X	X						

Product: MK-3475

Protocol/Amendment No.: Amendment 5, 21 October 2019

Trial Period	Screening Phase	Treatment Week/Cycle											End of Treatment		Post Treatment
Treatment Week/ Title	Screening Visit ^a	1	4	7	8	9	10	11	12	13	16	19	Discontinuation ^c	Safety FU ^c 20	Follow-Up Visit ^d
Scheduling Window (Days)	-28 to -1	+/- 3	+/- 3	+/- 1	+/- 1	+/- 1	+/- 1	+/- 1	+/- 1	+/- 3	+/- 3	+/- 3	At time of Discontinuation	30 days Post discontinuation	3,6,9,12,18,24 Post cyst
Clinical Procedures/ Assessments															
Restaging Ta T1 tumors/ Possible Transurethral Resection ⁱ	X														
Review Adverse Events ^j	X	X-----X													
Physical Exam ^k	X ^k	X	X	X			X			X	X	X	X ^k	X ^k	
Performance Status ^l	X			X						X		X	X	X	
Vital Signs and Weight	X	X	X	X	X	X	X	X	X	X	X	X	X	X	
ECG ^m	X														
Chest X-Ray ⁿ	X ^q														
Pulmonary Function Tests ^m	X														
Laboratory Procedures/ Assessments: Analysis provided by Local Laboratory															
CBC w/ differential	X	X ^r	X	X			X			X	X	X	X	X	
CMP	X	X ^r		X			X			X		X	X	X	
Urinalysis	X			X	X	X	X	X	X			X	X	X	X
T3, FT4, and TSH	X			X									X	X	
Pregnancy Test (Urine or β-HCG)	X														
PT/INR and aPTT ⁿ As clinically indicated	X											X			
Hepatitis Panel	X														

Product: MK-3475

Protocol/Amendment No.: Amendment 5, 21 October 2019

Trial Period	Screening Phase	Treatment Week/Cycle											End of Treatment		Post Treatment
Treatment Week/ Title	Screening Visit ^a	1	4	7	8	9	10	11	12	13	16	19	Early Discontinuation ^b	Safety FU ^c 20	Follow-Up Visit ^d
Scheduling Window (Days)	-28 to -1	+/- 3	+/- 3	+/- 1	+/- 1	+/- 1	+/- 1	+/- 1	+/- 1	+/- 3	+/- 3	+/- 3	At time of Discontinuation	30 days Post discontinuation	3,6,9,12,18,24 months Post cyst
Study Treatment															
BCG*				X	X	X	X	X	X						
MK 3475		X	X	X			X			X	X				
Efficacy Measurements															
Cystoscopy ^o	X											X			X
Biopsy (if clinically indicated) ^o	X											X			X
Tumor Biopsies/ Archival Tissue Collection/ Correlative Studies Blood															
Specimen Collection ^p		X ^r	X	X	X	X	X	X	X	X	X	X			X ^p

^aScreening Visit: No study required procedures should be conducted (unless part of routine care) prior to the signing of the informed consent document. Screening Visit laboratory procedures may be used for Day 1 Cycle 1 if completed within 10 days of Day 1 Cycle 1. Restaging imaging of CT urogram or CT/ MRI of abdomen/ pelvis that occurs within 90 days of study entry is acceptable.

^bEarly Discontinuation Visit: All Subjects who discontinue treatment early for any reason should undergo all procedures listed in the Flow Chart for Discontinuation Visit.

^cIf a subject has completed all study treatment, the subject should complete the 30 day Safety Follow-Up Visit procedures listed in the Flow Chart.

^dFollow-Up Visits should occur at approximately 3, 6, 9, 12, 18, and 24 months from Week 19 cystoscopy. It is expected that follow up data will be collected from routine office visits which generally occur every three months in this population. There may be a shift in schedules if the participant has been given maintenance therapy or was found to have a recurrence. Subject will complete final set

Product: MK-3475

Protocol/Amendment No.: Amendment 5, 21 October 2019

of Questionnaires at the 3 month visit. Follow-Up information may be collected via medical record and document review only. However, patient contact via phone or in person may occur if information is not available via chart review.

^eSubject Identification card may be given at any time after consent process has occurred and prior to treatment on Day 1 Cycle 1.

^fPrior and concomitant medications will include any medications taken within the 28 days prior to consent and through the safety visit and will include prescribed, over-the counter and herbal/alternative remedies.

^gPost-study treatment anti-cancer therapy and recurrence status may be collected through follow-up chart review.

^hQuestionnaires: AUA IPSS and QOL will be completed prior to any treatment or procedures scheduled for that visit.* To monitor for systemic dissemination of BCG infection, daily phone calls of days 2-4 of each cycle of BCG treatment (Weeks 7-12) will occur to monitor for fever and symptoms of systemic infection. Subjects will each be given an oral thermometer and a diary to record oral temperature twice daily (morning and evening) and to record any symptoms they may be having. The diary will be utilized Days 1-7 for each of the 6 BCG cycles (Weeks 7-12).

ⁱTrans-urethral Resections: All TURB will occur as part of SOC and as clinically indicated. Screening cystoscopy/TURBT window is 90 days prior to the start of treatment.

^jAdverse Events will be collected from time of main study informed consent through 30 days post last study drug infusion/treatment.

^kPhysical Exam: Full physical exams are required at screening and at the 30 day follow up. All other exams may be symptom directed.

^lPerformance status: ECOG performance status scale should be used to measure performance status.

^mECG, Chest X-ray, and Pulmonary Function Tests will be completed prior to Day 1 Cycle 1 and will only be repeated as clinically indicated.

ⁿPT/INR and aPTT will be completed prior to all resections/ possibly biopsies as standard of care. All other monitoring of PT/INR and aPTT will only be completed as clinically indicated (i.e. if on Coumadin).

^oCystoscopy will be performed as standard of care, but will be considered measures for efficacy. Biopsy will be performed as clinically indicated.

Product: MK-3475

Protocol/Amendment No.: Amendment 5, 21 October 2019

^pSpecimen Collection/Correlative studies: Whole blood, serum, and urine will be collected at time of consent or may be collected at any time prior to treatment on Day 1 of Cycle 1. Specimens for correlative study will also occur at each visit through Week 19, repeat cystoscopy (12 visits). Saliva will be collected only at baseline. Tumor tissue will only be collected at Week 19 biopsy, if a biopsy is clinically indicated at the time of cystoscopy. Specimen collection is requested at the 3, 6, 9, 12, 18, and 24 month follow up visits if subject is being treated locally at the site, though not required. Tissue will only be collected if a biopsy is clinically indicated at time of cystoscopy.

^qChest X-rays performed in the 90 days window prior to the screening visit are acceptable.

^rCBC, CMP, and correlative labs do not need to be repeated on Day 1 Cycle 1 if they were completed within 10 days prior to Day 1 Cycle 1 during screening.

